## **2.2 Treatment Assignment**

Eligible subjects will be randomized (2:1) to either ETV or PBO.

At the start of the screening period, the investigative staff will call the Randomization Center designated by the sponsor to register the subject and to obtain a subject number or patient identification number (PID). For subjects who meet the protocol defined eligibility criteria during screening, the investigative staff will again call the Randomization Center for the subject to be randomized into a blinded treatment assignment based on the subject’s age at the time of randomization. The subject will be assigned bottle numbers according to the randomization scheme. For each study visit, the site will need to call the Randomization Center for container assignments.

A randomized block design stratified by age group will be used. The target enrollment will be 30 subjects for each age group with a minimum requirement of 18 subjects to support the primary analysis for Primary Cohort.

## **2.3 Blinding and Unblinding**

The subject, investigator and Bristol-Myers Squibb personnel involved in the conduct of the study will be blinded to treatment assignment. Designated staff of Bristol-Myers Squibb pharmacokinetics and modeling departments, as well as personnel from the central and analytical laboratories, will be unblinded to treatment assignments in order to minimize unnecessary analysis of samples from subjects receiving placebo.

A pharmacist at Bristol-Myers Squibb not involved in the study design, assessment, or analyses will be given access to the treatment codes to permit efficient drug distribution. The treatment codes will be maintained in a password-protected file which cannot be accessed by the study personnel or subjects.

HBV DNA results from Day 1 through Week 96 will be blinded to the investigator. Any subject who has achieved HBeAg seroconversion by Week 96 shall remain blinded to their randomized treatment assignment except in the event of a change in clinical status for which knowledge of the randomized arm is critical to subject management. Subjects who have not yet achieved HBeAg seroconversion by Week 96 will be unblinded on an individual basis, as needed in order to determine their further management. Refer to Protocol Section 5.4 for more details on blinding and unblinding.

## **2.4 Protocol Amendments**

### **2.4.1 Amendment 1 (Country Specific - Brazil Only)**

The purpose of this amendment is to incorporate changes requested by the Brazilian Research Ethics Commission (CONEP) regarding post study access to therapy. This country-specific amendment applies to all subjects enrolled in Brazil.

### **2.4.2 Amendment 2**

- The purpose of this amendment is to make the following changes to the protocol:
- Augment the number of randomized subjects from 123 to 180 and increase the estimated number of participating study centers.
- Change the entry ALT entry criteria from  $\geq 1.3$  to  $\geq 1.5 \times$  upper limit of normal (ULN), increase the minimum time span between the 2 pre-randomization ALT measurements from 4 to 8 weeks, and exclude other reasons for elevated ALT.
- Specify the early unblinding and mechanism for doing so if subjects demonstrate significant worsening of HBV clinical symptoms or increases in ALT. The role of the DMC in safeguarding subjects is clarified.
- Specify additional analyses that will be conducted as key secondary and exploratory endpoints.
- Modify the blood volume collected at some visits due to minimum fill volume requirements of available specimen collection tubes.
- Summarize the plan for PK/PD analyses that will integrate Studies AI463-028 and AI463-189.
- Add Tanner Stage assessment and analysis.

### **2.4.3 Amendment 3 (Site Specific - Site -038)**

This amendment has been required by the Ethics Committee (EC) at Rambam Medical Center and it documents the standard of care practices that will take place for all patients prior to possible study enrollment at this site. Per the site's usual standard of care, a liver biopsy will be performed for any patient with a pre-screening ALT  $> 3 \times$  ULN. Based on the histological findings, those patients for whom possible randomization to PBO is judged not to be in their best interest, will not be consented and enrolled in study AI463-189. This site-specific amendment applies to the pre-enrollment practices at site -038 as requested by their EC.

### **2.4.4 Amendment 4 (Country Specific - India only)**

The purpose of this amendment is to restrict the age of study participants enrolled in this study at sites in India, as required by the Directorate General of Health Services in the Office of Drugs Controller General (India). This amendment will document the modified inclusion criteria for India sites; restricting enrollment to male and female adolescents aged  $> 12$  to  $< 18$  years (oldest age group).

Sites in other participating countries will enroll subjects 2 to < 18 years of age. Therefore, the description of the age groups written in other sections of the protocol will not be modified in this amendment.

### **2.4.5 Amendment 5**

The purpose of this amendment is to address the potential safety issues associated with extreme elevations of ALT due to acute exacerbation of CHB by providing emergency access to rescue open-label ETV for subjects who cannot access acceptable alternative anti-HBV therapy.

## **2.5 Data Monitoring Committee**

There will be a data monitoring committee (DMC) for this study. The DMC shall have access to unblinded data on at least an annual basis, including but not limited to following: the frequency and spectrum of serious adverse events; Grades 3 to 4 laboratory abnormalities; occurrence of malignancies; and other select adverse events of interest. The DMC shall act as an advisor to the sponsor and have responsibility for safeguarding the subjects' interests. The DMC shall bring any safety concerns to the attention of the sponsor so that the sponsor can review the data and prepare appropriate communications to the Regulatory Authorities. A separate charter describes the membership and activities of the DMC.

## **3 OBJECTIVES**

### **3.1 Primary**

To compare the proportion of subjects in each treatment group who achieve a combination of HBV DNA suppression and HBeAg seroconversion (undetectable HBeAg AND detectable anti-HBe antibodies) at Week 48.

### **3.2 Secondary**

- Assess the serologic response rates (defined as HBsAg loss and/or seroconversion; and HBeAg loss and/or seroconversion) including durability of response off treatment;
- Assess the virological response rates;
- Assess the biochemical response rates;
- Assess ETV resistance rates;
- Evaluate the long-term safety of ETV use in pediatric patients.

## **4 ENDPOINTS**

### **4.1 Primary Endpoint**

- The proportion of subjects who achieve: 1) HBV DNA < 50 IU/mL (approximately 300 copies/mL) using the Roche COBAS® TaqMan HBV Test for use with the High Pure System (HPS) assay; **and** 2) HBeAg seroconversion (undetectable HBeAg AND detectable anti-HBe antibodies) at Week 48 of study treatment.

## 4.2 Key Secondary Endpoints

- Proportion of subjects with HBV DNA < 50 IU/mL using the Roche COBAS® TaqMan HBV Test for use with the High Pure System (HPS) assay at Week 48;
- Proportion of subjects with serum ALT  $\leq 1 \times$  ULN at Week 48;
- Proportion of subjects with HBV DNA < limit of quantification (LOQ; 29 IU/mL) using the Roche COBAS® TaqMan HBV Test for use with the High Pure System (HPS) assay at Week 48;
- Proportion of subjects with HBeAg seroconversion (undetectable HBeAg and presence of anti-HBe antibodies) at Week 48;
- Proportion of subjects who achieved sustained HBeAg seroconversion during off-treatment follow-up among subjects who achieved HBe seroconversion (undetectable HBeAg and presence of anti-HBe antibodies) at end of treatment.

## 4.3 Other Secondary Endpoints

- The number and percent of subjects with adverse events (including palatability issues), serious adverse events (SAEs), discontinuations due to adverse events, and HBV disease progression through Week 48;
- Proportions of subjects with HBeAg loss at Weeks 48 and 96;
- Proportion of subjects with HBeAg seroconversion at Week 96;
- Proportion of subjects who maintained HBeAg seroconversion at Week 96 (end of blinded therapy) among subjects who achieved HBeAg seroconversion at Week 48;
- Histological analysis among subjects with available liver biopsy.

[REDACTED]

- [REDACTED]

#### 4.5 PK Endpoints

PK parameters include Cmin, Cmax and Tmax.

### 5 SAMPLE SIZE AND POWER

One hundred and twenty-three (123) subjects (randomized 2:1 to ETV vs placebo) in this study provide 90% power to show superiority of ETV versus PBO assuming a response rate for the primary endpoint HBV DNA by PCR < 50 IU/mL (approximately 300 copies/mL) and HBeAg seroconversion of 20% for ETV and 1% for PBO. A two-sided significance level of 0.05 is used. Subjects who either discontinue from study treatment prior to Week 48 or have having missing Week 48 HBV DNA or HBeAg serology measurement are considered as failures at Week 48 (Non-Completer = Failure). The efficacy estimate for ETV is derived from an analysis of the identical endpoint (HBV DNA by PCR < 300 copies/mL and HBeAg seroconversion) in the pivotal Phase 3 study of HBeAg-positive subjects, (AI463022). The efficacy estimate for PBO is derived from evidence in the literature which shows that whereas spontaneous seroconversion occurs at a relatively high rate in children, viral replication remains detectable using sensitive PCR assays. The results of the Gilead Sciences' pediatric CHB study (GS 518) support this estimate; 3 of 57 placebo treated subjects (5.3%) achieved HBeAg seroconversion, but only 1 of 58 subjects (1.7%) achieved HBV DNA < 2.23 log10 copies/mL at Week 48.

This sample size also fulfills the requirement that the ETV integrated pediatric safety database has at least 100 pediatric subjects who have received ETV for at least 48 weeks; this database will be comprised of subjects currently enrolled in study AI463-028 and from this study (AI463-189).

Currently 24 nucleoside naive subjects are enrolled in AI463-028; all 24 would have had 48 weeks of safety data collection by the time study AI463-189 reaches Week 48.

Based on the original planning for study AI463-189, it is estimated that 175 subjects will be enrolled to have approximately 123 subjects randomized (approximately 30% screen failure rate). Randomization is 2:1 (ETV 82: PBO 41); assuming a 10% drop out rate per year and even enrollment for 2 calendar years, approximately 72 ETV randomized subjects will have 48 weeks of safety data by study Week 144. This brings the number of subjects that will be included in the integrated safety database at the end of study Week 144 to approximately 96 subjects.

Additional safety data will be contributed by PBO randomized subjects switching to open label ETV at study Week 52. Because it is expected to take 2 calendar years to randomize 123 subjects

and assuming steady enrollment over that time frame, the last PBO randomized subject will be completing Week 48 by study week 144. Assuming a 10% drop out per year, 18 of the 20 subjects randomized to PBO during the first calendar year will reach Week 48 by study Week 96; 16 of these 18 will be switched to open label ETV (assuming a 10% HBeAg seroconversion rate on PBO). With a 10% drop out rate per year, 14 of these 16 will be completing 48 weeks of open label ETV by study Week 144 and will be added to the integrated safety database. This will bring the number of subjects in the integrated safety database with at least 48 weeks of ETV exposure after two years of enrollment to approximately 110 subjects.

While the analysis of the primary endpoint is based on a randomized sample size of 123, the size of the overall study population has been augmented to 180 randomized subjects in order to meet the requirement of a health authority. Therefore the final safety dataset as described in the previous 2 paragraphs will also be augmented. The accrual of the first 123 randomized subjects is expected to take 2 years. Thereafter, the enrollment will remain open until 180 subjects are randomized. Additional re-analyses will be performed on the augmented population.

## 6 STUDY PERIODS, TREATMENT REGIMENS AND POPULATIONS FOR ANALYSES

### 6.1 Study Periods

Study periods for efficacy and safety analyses are defined as follows:

- **Pre-treatment period** begins at the first visit until initiation of study therapy.
- **On-treatment period** begins after the first day of study therapy and ends at the last dose of study therapy plus 5 days.
- **ETV treatment period** begins after the first day of active ETV and ends at the last dose of active ETV plus 5 days.
- **Off-treatment follow-up period** begins on the last dose of study therapy plus 6 days and ends at the start of alternative anti-HBV therapy minus 1 day.
- **Long-term follow-up period** begins on the last dose of study therapy plus 6 days until the end of the study.
- **Alternative ETV follow-up period** begins on the later of the last dose of study therapy plus 6 days and the start of alternative ETV therapy, until the end of the study.

Note that rescue open-label ETV is considered alternative anti-HBV therapy. See [Section 8.9](#) for additional conventions.

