Duration of Study: 5 years, or until the last study subject treated with rescue open-label ETV for an extreme elevation of ALT due to acute exacerbation of CHB completes 48-weeks of off-treatment follow-up; whichever is later.

Number of Subjects per Group: Approximately 180 total [randomized 2:1 to ETV (120) and Placebo (60)]; the target enrollment will be 30 subjects for each age group, with a minimum requirement of 18 subjects.

Study Population: Male and female patients 2 to < 18 years of age with a history of chronic HBV infection (defined as HBsAg positive at the Screening visit and on at least one other occasion \geq 24 weeks prior). All subjects must be nucleos[t]ide naive (< 12 weeks of prior therapy with any nucleos[t]ide antiviral agent with activity against hepatitis B virus and no anti-HBV treatment within 24 weeks of screening); have detectable HBeAg AND no detectable anti-HBe antibodies; have active viral replication and biochemical evidence of active hepatitis with compensated liver function.

Investigational Product(s), Dose and Mode of Administration, Duration of Treatment with Investigational Product(s): ETV dosing at 0.015 mg/kg/day up to a maximum dose of 0.5 mg/day using oral solution or tablets. During the treatment period, ETV dosing will be for a maximum of 144 weeks. Placebo (reference therapy) dosing with oral solution or tablets will be for a maximum of 96 weeks. A subject who experiences an extreme elevation of ALT due to acute exacerbation of CHB may be provided with rescue open-label ETV for up to 96 consecutive weeks at investigator's discretion and after discussion and approval by the BMS Central Medical Monitor. Rescue open-label ETV will be limited to those subjects who do not have access to acceptable alternative anti-HBV therapy.

Study Assessments and Primary Endpoints:

To test the study hypothesis, the primary endpoint of the analysis will be the proportion of subjects who achieve the composite of: 1) HBV DNA < 50 IU/mL (approximately 300 copies/mL) using the Roche COBAS[®] TaqMan HBV Test for use with the High Pure System (HPS) assay; and 2) HBeAg seroconversion (undetectable HBeAg AND detectable anti-HBe antibodies) at Week 48.

Key Secondary Endpoints:

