4.1.2 Subjects Experiencing Significant Elevations Of ALT Due To Acute Exacerbation of CHB

A subject who experiences an extreme elevation of ALT due to acute exacerbation of CHB should be carefully managed at the discretion of the primary investigator. Additional laboratory testing and frequent clinical evaluations are recommended (See [Figure 5.3.2.1](#)).

- An extreme elevation of ALT due to acute exacerbation of CHB is defined as:
 - a serum ALT > 1,000 U/L,OR
 - an elevation in serum ALT > 20x ULN WITH associated clinical or laboratory findings suggestive of hepatic dysfunction,
- Upon investigator request and after discussion and approval by the BMS Central Medical Monitor:
 - A subject who experiences an extreme elevation of ALT due to acute exacerbation of CHB will be provided access to rescue open-label ETV.

The choice of anti-HBV therapy to be used to treat an extreme elevation of ALT due to acute exacerbation of CHB remains at the discretion of the investigator. Only open-label ETV will be provided by the sponsor, and will be limited to those subjects who do not have access to acceptable alternative anti-HBV therapy. Subjects started on rescue open-label ETV will be provided the drug for up to 96 consecutive weeks. Upon completion of the rescue open-label ETV course, subjects will remain on study as part of the LTFU phase until they complete a total of 5 years of study participation from the start of blinded treatment or 48 weeks beyond the completion of rescue open-label ETV; whichever is later. During this time, subjects may be treated with alternative anti-HBV therapy at the discretion of their primary investigator. The sponsor reserves the right to terminate access to rescue open-label ETV if any of the following occur: a) the study is terminated due to safety concerns; b) the subject can obtain medication from a

government sponsored or private health program; or c) therapeutic alternatives become available in the local market.

Specific decisions regarding the management of an extreme elevation of ALT due to acute exacerbation of CHB remain at the discretion of the subject's primary investigator but access to rescue open-label ETV must be discussed with and approved by the BMS Central Medical Monitor.

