For PBO-treated subjects who receive open-label ETV, baseline is used during blinded dosing, while ETV baseline is used during open-label ETV dosing.

Laboratory abnormalities by toxicity grade (Grade 1 - 4; Grade 3 - 4) are also summarized by treatment regimen and EOD status (all, normal, abnormal) for the first 2 follow-up cohorts: (1) off-treatment follow-up for off-treatment follow-up subjects in the Post-Year 1 Safety Cohort; (2) long-term follow-up for long-term follow-up subjects in the Post-Year 1 Safety Cohort.

Laboratory abnormalities by toxicity grade (Grade 1 - 4; Grade 3 - 4) are also summarized by treatment regimen during alternative ETV follow-up for alternative ETV follow-up subjects in the Post-Year 1 Safety Cohort.

Emergent laboratory abnormalities by toxicity grade (increased to Grades 1, 2, 3 and 4) are also summarized analogously by treatment regimen and EOD status for the first 2 follow-up cohorts. Emergent abnormalities are those with a higher toxicity grade than the EOD toxicity grade.

Select laboratory elevations and abnormalities are summarized relative to the EOD value for the 3 follow-up cohorts. In addition, elevations of liver function tests (including ALT flares, defined as ALT > 2 x reference and > 10 x ULN) during the follow-up periods are summarized using the reference value (REF) (ie, minimum of the baseline and EOD values) for the 3 follow-up cohorts. Note that for PBO-treated subjects who receive open-label ETV, reference is the minimum of the ETV baseline and EOD values.

ALT multiples of ULN and HBV DNA values are plotted over time for each subject who had an ALT flare on study. The duration of an ALT flare is measured from the first ALT measurement meeting the ALT flare criteria to resolution, defined as (1) the first ALT  $\leq$  baseline or  $\leq 5$  x ULN on treatment, or (2) the first ALT  $\leq$  reference or  $\leq 5$  x ULN during follow-up. If (1) and (2) are not met, an ALT flare is considered unresolved, and the last ALT measurement is used to estimate duration.

The time to and duration of ALT flares (weeks) during off-treatment follow-up are summarized for off-treatment follow-up subjects in the Post-Year 1 Safety Cohort (limited to ETV, PBO OL, and All ETV). Analyses are based on the first ALT flare during off-treatment follow-up.

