- Dose end date of active ETV is the dose end date of study therapy for ETV-randomized subjects and the dose end date of open-label ETV for PBO-randomized subjects. This date is used to assess time on active ETV.
- Last dose date of active ETV is the dose end date of active ETV derived only when the last dose date of study therapy is not missing.
- Start date of rescue open-label ETV is the earliest start date of rescue open-label ETV identified from valid dosing records, ie, non-missing start date and total dose > 0, from rescue open-label ETV study medication CRFs.
- Start date of alternative ETV therapy is the earliest start date of (1) rescue open-label ETV, or (2) concomitant ETV taken on treatment or during long-term follow-up.
- Start date of alternative anti-HBV therapy is the earliest start date of (1) rescue open-label ETV, or (2) concomitant anti-HBV medication taken on treatment or during long-term follow-up.
- Last contact date is the death date, if it exists, or the latest of the following dates: randomization; first or last dose of study therapy; adverse event onset or resolution; hepatitis B related diagnosis; laboratory test (safety, pregnancy, serology and virology); liver biopsy; physical measurement; physical exam; neurologic exam; vital sign; non-study medication start or stop; last contact from end of treatment or end of study subject status; Tanner staging.

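### The alternative ETV follow-up period has no end tied to the last ETV dose, so events on rescue ETV and after it are pooled and post-rescue follow-up is never summarised separately

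*SAP*

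**What the plan says.** SAP 6.1 starts the alternative ETV follow-up period at the later of two dates: 6 days after the last dose of study therapy, and "the start of alternative ETV therapy, until the end of the study". SAP 8.9 supplies the opening date: "Start date of alternative ETV therapy is the earliest start date of (1) rescue open-label ETV, or (2) concomitant ETV" taken on treatment or in long-term follow-up. It gives no matching stop date, and it leaves rescue ETV out of the study-therapy dose dates.

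The off-treatment follow-up period "ends at the start of alternative anti-HBV therapy minus 1 day". Rescue closes it: "Note that rescue open-label ETV is considered alternative anti-HBV therapy". The long-term follow-up period "begins on the last dose of study therapy plus 6 days until the end of the study", so it contains everything that happens on and after rescue.

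Protocol 4.1.2 limits the course: "Subjects started on rescue open-label ETV will be provided the drug for up to 96 consecutive weeks". The child then stays on study to 5 years or to 48 weeks after rescue, whichever comes later, and may receive other anti-HBV therapy. The protocol synopsis (Duration of Study) treats this stretch as off treatment: the study runs 5 years or until the last rescued subject "completes 48-weeks of off-treatment follow-up; whichever is later".

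SAP 7.6.2 (SAEs), 7.6.5 (AEs) and 7.6.6.1 (laboratory) all report on the window. Graded laboratory abnormalities, for example, "are also summarized by treatment regimen during alternative ETV follow-up for alternative ETV follow-up subjects in the Post-Year 1 Safety Cohort".

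**The concern.** Every other dosing-related period in SAP 6.1 stops shortly after the drug does. This one does not, although rescue has a fixed maximum length and the protocol requires follow-up after it.

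Two safety questions are natural for these children, who have already had an extreme ALT elevation: how they fared while taking rescue ETV, and whether hepatitis flared once it stopped. Protocol 1.5 records that exacerbations have been seen both during ETV treatment and in follow-up after it. A single window running from the first alternative ETV dose to the end of the study puts both kinds of event in the same row of the same table. A reader of that table cannot tell them apart.

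**Working it through.** **Step 1. Where each SAP 6.1 period ends.**

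| Period | Ends |
|---|---|
| On-treatment | last dose of study therapy + 5 days |
| ETV treatment | last dose of active ETV + 5 days |
| Off-treatment follow-up | day before alternative anti-HBV therapy starts |
| Long-term follow-up | end of study |
| Alternative ETV follow-up | end of study |

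Off-treatment follow-up has no rule to reopen it. After rescue stops, a child is therefore in the last two periods only, and neither one separates time on rescue from time after it.

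**Step 2. How events are collected.** Protocol Table 6.1 (footnote e) asks for AEs at every visit on rescue, but otherwise only at long-term follow-up Week 6. Protocol 7.3.3 asks for all AEs on rescue. Otherwise in long-term follow-up it asks only for those related to giving or stopping study drug, in subjects not on commercial anti-HBV therapy. The pooled AE table thus mixes two levels of ascertainment. SAEs are less affected, because Protocol 7.3.1 has them reported throughout long-term follow-up.

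**Step 3. How laboratory changes are judged.** SAP 7.6.6.1 compares select laboratory elevations in all three follow-up cohorts with the end-of-dosing (EOD) value. SAP 8.5 ties EOD to the last dose of study therapy, which excludes rescue. Liver-test elevations and ALT flares use the minimum of baseline and EOD, or of ETV baseline and EOD for placebo subjects who received open-label ETV. No end-of-rescue value serves as a reference. Time to flare and duration of flare are summarised for off-treatment follow-up only, so post-rescue flares are left out.

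**Step 4. How much of the window lies after rescue.** The plan states no figure to reproduce, so this is an illustration. Inputs from the documents are 264 weeks of planned participation (Protocol 4.1), at most 96 weeks of rescue, and at least 48 weeks on study afterwards (Protocol 4.1.2). The start week W and the course length D are assumptions, apart from the 96-week maximum. I also assume completed follow-up and no further ETV, and I ignore the 5-day lag.

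End of study E = max(264, W + D + 48). Post-rescue share = (E − W − D)/(E − W).

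| W | D | E | Post-rescue weeks | Window | Share |
|---|---|---|---|---|---|
| 30 | 96 | 264 | 264 − 126 = 138 | 234 | 59% |
| 30 | 48 | 264 | 264 − 78 = 186 | 234 | 79% |
| 48 | 96 | 264 | 264 − 144 = 120 | 216 | 56% |
| 96 | 96 | 264 | 264 − 192 = 72 | 168 | 43% |
| 120 or later | 96 | W + 144 | 48 | 144 | 33% |

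Under these assumptions, between a third and well over half of the window falls after rescue.

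**The case against.** The best defence is that the window is meant to be an ever-exposed one. SAP 6.3 admits anyone with at least one dose of alternative ETV, and SAP 7.6 lists the cohort under follow-up safety, apart from the on-treatment cohorts and for select endpoints only. Protocol 8.4.2 itself ends off-treatment follow-up when alternative therapy starts, and Protocol 4.1.2 places the post-rescue time in the long-term phase. The SAP follows that structure.

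This answers several stronger readings that a reader might infer:

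- *Post-rescue data are never analysed.* They are. They enter the long-term follow-up summaries of SAEs, AEs, laboratory abnormalities and flares, and the combined summaries of disease progression, malignancy and growth. Deaths are listed regardless of period, and ALT and HBV DNA are plotted for each subject with a flare. What is missing is a separate summary.
- *The SAP reports these events as safety on ETV.* It calls the period follow-up and does not say that. Exposure-adjusted rates are planned only for the on-treatment cohorts, so no person-time denominator is distorted.
- *The safety questions cannot be answered at all.* The flare plots and rescue dosing records allow case-by-case review. Flares after study ETV have their own off-treatment analysis.
- *The post-rescue time is off drug, and 33% is a floor.* Other anti-HBV therapy is allowed after rescue, and alternative ETV includes concomitant ETV that may continue. Early withdrawal or continued ETV could bring the share to zero.

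The objection also holds that the affected output is descriptive and probably concerns few children, since rescue needs an extreme ALT elevation, no acceptable alternative therapy and Medical Monitor approval. The documents give no number.

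The core point still stands. An ever-exposed window may be kept, but the plan has neither an on-rescue window nor a post-rescue window beside it.

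**Conclusion.** The point holds as a gap in separation, not as an omission of data. No planned summary distinguishes events on rescue or alternative ETV from events after it. Post-rescue flares are judged against study-therapy values and left out of the time-to-flare and duration analysis, and non-serious AEs are pooled across two collection rules.

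The 33% and 59% shares describe time after rescue, not untreated time. They depend on the assumed start week, a full 96-week course, completed follow-up and no further ETV. How many children this touches is unknown. The importance is low to moderate, and no primary or key secondary comparison changes.

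**What to change.** - SAP 8.9: derive the last dose date of rescue or alternative ETV, with a stated rule for concomitant ETV recorded as continuing and for a gap between rescue and commercial ETV.
- SAP 6.1: split the period into on-alternative-ETV, ending at that date plus 5 days, and post-alternative-ETV, running from plus 6 days to the next anti-HBV therapy or the end of the study. This is the SAP's own 5-day and 6-day convention.
- SAP 7.6.2, 7.6.5 and 7.6.6.1: report SAEs, AEs, laboratory abnormalities and ALT flares for each part. Use an end-of-rescue reference for post-rescue laboratory elevations, and add a note to the AE table that collection differs between the two parts.

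The existing long-term follow-up summaries can stay. The cost is SAP wording, one more derived date and some programming. Rescue dosing forms and non-study medication stop dates are already part of the data; that the rescue form records stop dates, as the open-label form does, is an assumption to confirm. The downside is smaller cells in a descriptive table.
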